3.4 Study Timeline

In Part A, no follow up is planned.

In Part B, patients will be followed until discontinuation of treatment with PI3K/mTOR pathway inhibitor.

The anticipated accrual period is 24 months (~ 1-2 patients/month). Duration of follow up will vary by tumor type but is expected to average approximately 6 months, leading to an estimated total study duration of 30 months.

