3.1 Characteristics

This is a single center prospective imaging study investigating the utility of hyperpolarized C-13 pyruvate/metabolic MR imaging. The current protocol will serve as a companion imaging biomarker study paired with therapeutic trials of PI3K/mTOR pathway inhibitors (e.g. CUDC-907, BYL719) as well as a stand-alone protocol for patients treated with standard-of-care PI3K pathway targeting therapies (eg. everolimus).

In Part A (run-in feasibility phase), patients will undergo imaging at single time point, without paired tumor biopsy. There will be follow up imaging or requirement for treatment with PI3K/mTOR pathway inhibitor. Iterative adjustment of radiofrequency coil geometry and imaging sequences will be undertaken to optimize intra-tumoral hyperpolarized pyruvate/lactate signal-to-noise ratio during Part A of the study.

In Part B, patients will undergo paired baseline hyperpolarized C-13 pyruvate imaging + optional tumor biopsy, then initiate treatment with agent inhibiting the PI3K/mTOR pathway. After 21 days (+/- 14 days), patients will undergo repeat hyperpolarized C-13 pyruvate MR imaging + optional paired tumor biopsy. Patients will subsequently be treated with PI3K/mTOR pathway inhibitor until disease progression, unacceptable toxicity, or patient/physician decision to discontinue therapy.

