5.7 Every 6-12 weeks (Part B Only)

Patients will undergo standard disease assessments including standard staging scan every 6-12 weeks per standard of care or per protocol on therapeutic clinical trial. Patients will be followed discontinuation of PI3K/mTOR pathway inhibitor therapy, due to disease progression, unacceptable toxicity, or patient/physician decision to discontinue therapy.

Table 2: Schedule of Study Procedures and Assessments

Period/ Procedure	Screening (28 Days)	Cycle 1 Day 1	Day 21 (+/- 14 days)	Day 28 (+/- 14 days)	Every 6-12 Weeks	Disease Progression
Informed consent	x					
Baseline conditions	х					
AE assessment	х		Х			
Concomitant medications	х		х			
Physical exam	Х					
Vital signs	Х		Х			
Medical history/ Demographics	х					
Tumor Assessment by Standard Scans (within 3 months of C1D1)	Х				X (Part B only)	
Performance status	х					
CBC w/ Diff	х					
Blood chemistry	х					
HP C- 13/metabolic MRI	х		X (Part B only)			
ECG/EKG	х					
		Pai	rt B Only			•
PI3K/mTOR Pathway Inhibitor						
Tumor biopsy (Optional)	Х			х		

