7.8 Analytic Plan

7.8.1 Analysis Population

All data from all subjects dosed in the study will be included in all listings, plots, summary tables, and statistical analyses when appropriate. Missing values will not be substituted by estimated values, but treated as missing in the statistical evaluation.

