7.8.3 Analysis of Secondary and Exploratory Endpoints

For the purposes of analyzing the association between percent change from baseline in intratumoral peak lactate/pyruvate ratio on HP MRI with subsequent clinical outcomes, the cohort will be dichotomized by the median percent change. The objective response rate by RECIST 1.1 criteria and clinical benefit rate (response or stable disease for > 24 weeks) will be compared between dichotomized groups using the chi-squared test. The log rank test will be used to compare the radiographic progression-free survival between the two groups.

Safety analyses will be performed for all patients having received a dose of HP C-13 pyruvate. The study will use the NCI CTCAE v4.0.

Analyses will be performed to compare the HP MR markers with immunohistochemical and enzyme expression and activity data from biopsy tissue to investigate the molecular and physiological underpinnings of the HP ¹³C MR data. When both the HP biomarker and molecular biomarker (LDHA activity) are continuous variables, Spearman's rank correlation coefficient will be used to investigate a possible correlation between them. If the outcome is categorical (e.g. immunohistochemistry score 0-1+ vs 2-3+ for pS6, pAkt, LDHA, and MCT 1/4 expression), the HP biomarker distributions will be compared between the two categories using the Mann-Whitney test.

Intra-patient reproducibility of HP lac/pyr ratio for patients who undergo repeated dose imaging studies will be descriptively reported using summary statistics (mean difference, standard deviation, range).

No adjustment will be made for multiple comparisons for the analysis of the secondary and exploratory endpoints.

8 Study Management

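### Part B follow-up ends when the inhibitor is stopped for any reason, so progression-free survival events and 24-week clinical benefit status are lost for patients who stop before progression

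*Combined protocol and SAP*

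**What the plan says.** Section 3.4 sets the end of follow-up: "In Part B, patients will be followed until discontinuation of treatment with PI3K/mTOR pathway inhibitor". The synopsis gives the same rule. Section 5.7 repeats it with the reasons (a word has dropped out, but the sense is clear beside 3.4): "Patients will be followed discontinuation of PI3K/mTOR pathway inhibitor therapy, due to disease progression, unacceptable toxicity, or patient/physician decision to discontinue therapy". Section 3.1 lists the same three reasons for ending treatment. Section 3.4 adds: "Duration of follow up will vary by tumor type but is expected to average approximately 6 months".

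Section 7.8.3 splits the cohort at the median percent change in the lactate/pyruvate ratio. It states "The log rank test will be used to compare the radiographic progression-free survival between the two groups", and it compares objective response and clinical benefit by chi-squared test. Clinical benefit means a response, or stable disease lasting more than 24 weeks.

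No section provides for recording progression or survival after a stop without progression. Section 7.8.3 gives no PFS censoring rule, no rule for a patient who stops before week 24 without progression, and no sensitivity analysis. The only general rule is in 7.8.1: "Missing values will not be substituted by estimated values, but treated as missing in the statistical evaluation".

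**The concern.** The follow-up rule and the endpoints do not fit together. PFS needs observation to progression or death, and stable-disease benefit needs observation past week 24. The protocol stops looking when the drug stops, and two of its three reasons for stopping are not progression.

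Two things are at stake for the secondary objective of linking the imaging change to clinical outcome. The first is information: events and benefit classifications are lost from a cohort of only 30. The second is possible bias. The log-rank test assumes that censoring is unrelated to prognosis within each group. The imaging change is proposed as a measure of pathway inhibition, so toxicity stops could plausibly track it, and physician-decision stops could plausibly come shortly before documented progression. The data as planned could neither detect nor correct this.

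**Working it through.** **Inputs from the documents.** Part B has 30 patients (7.3). A median split gives 30/2 = 15 per group. Average follow-up is about 6 months (3.4), and the benefit threshold is 24 weeks (7.8.3). The plan states no event count, hazard ratio or power for PFS, so there is no figure of its own to reproduce here. Its timeline does reproduce: 24 + 6 = 30 months.

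**Nearness to the threshold.** 6 × 52/12 = 26 weeks, and 26 − 24 = 2 weeks. Average follow-up barely passes the point at which stable-disease benefit is decided.

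**Loss of events.** With equal groups and two-sided 5%, power = Φ(√d × |ln HR|/2 − 1.96), where d is the number of events. At HR 0.5:

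- d = 30: √30 × 0.693/2 − 1.96 = 1.898 − 1.96 = −0.062, power 47.5%.
- d = 21 (30 × 0.7): 1.588 − 1.96 = −0.372, power 35.5%.

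| Stopped before progression (assumed) | Events | HR 0.5 | HR 0.4 | HR 0.33 |
|---|---|---|---|---|
| none | 30 | 47.5% | 70.9% | 85.9% |
| 20% | 24 | 39.7% | 61.2% | 77.5% |
| 30% | 21 | 35.5% | 55.5% | 71.9% |

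This assumes that everyone else is followed to progression or death. The loss needs no assumption about why patients stop.

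**24-week status.** Assume exponential PFS with median 4 months, so the progression hazard is h = ln 2/4 = 0.173 per month. Let stops without progression occur independently at rate λ per month. With 24 weeks = 5.54 months, the share stopping before week 24 without progression is λ/(λ + h) × (1 − exp(−(λ + h) × 5.54)). The true share progression-free at 24 weeks is 38%.

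| λ per month | Stop before week 24, no progression | Share if counted as failures | Share if excluded |
|---|---|---|---|
| 0.02 | 7% | 34% | 37% |
| 0.04 | 13% | 31% | 35% |
| 0.08 | 24% | 25% | 32% |

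In 30 patients that is about 2, 4 or 7 people. The model has no responses, so it is an upper bound on those with undetermined benefit. The result depends on a counting rule that the plan does not give.

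**Bias in the group comparison.** The simulation assumes no true difference, 15 v 15, exponential PFS with median 24 weeks, stopped patients censored 6 weeks before their event, log-rank rejection at |z| > 1.96, and 4,000 trials per scenario. Three separate runs gave:

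| Early stops, group 1 v group 2 | Apparent HR | False-positive rate |
|---|---|---|
| full follow-up | no bias | 6% |
| 20% v 10% | 0.89-0.91 | 6-7% |
| 30% v 10% | 0.80-0.81 | 9% |
| 40% v 10% | 0.70 | 12-12.5% |
| equal, 20-40% in both | 1.00-1.01 | 5-6% |
| 20-40% v 10%, unrelated to progression | 0.99-1.01 | about 6% |

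Changing the lead time to between 3 and 12 weeks moved the three biased hazard ratios to 0.90-0.92, 0.79-0.83 and 0.68-0.74. A looser model, with stopping and progression times only correlated and median PFS 4 months, gave a false-positive rate of 9.7% in its most extreme case (0.12 v 0.02 stops per month, correlation 0.8) and 6.2% at 0.08 v 0.02 with correlation 0.6.

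**The case against.** **An on-treatment endpoint may be intended.** Section 7.2 words the association endpoint as outcomes while on inhibitor therapy, and follow-up to discontinuation fits that. Counting PFS after a stop brings in time off drug or on another treatment, which is a different question for a pathway biomarker. This stands in part: which version is the main analysis is for the sponsor to choose. It does not remove the gap, because even an on-treatment PFS needs a rule saying whether a stop is censored or is an event, and 7.8.3 has none.

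**Therapeutic-trial procedures take precedence (5.4).** Co-enrolled patients may therefore be scanned for longer. But nothing brings those results into this study, and patients on standard-of-care therapy are not covered.

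**The comparison is weak under any rule.** With all 30 events, power at HR 0.5 is still only 47.5%. True, and a reason to keep the point in proportion, but not a reason to give up events that routine care may already be recording.

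**Bias is not shown.** A reader might infer that the follow-up rule amounts to informative censoring and that PFS will flatter the group with the larger imaging decline. The documents do not support that. They give no stop rates, no imbalance between groups, no link between stopping and coming progression, and no rule that stops are censored at all. The opposite imbalance would bias the other way. The simulated bias disappears when either condition is removed, and placing every stop shortly before progression is close to a worst case.

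**Conclusion.** The point holds as a mismatch between follow-up and endpoints. Followed exactly, the protocol loses PFS events for every patient who stops before progression, and 24-week benefit status for those who stop before week 24 without a response. A patient who responded before stopping is already classified, so it would be too strong to say that every early stop leaves benefit undefined.

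The information loss is unconditional in kind; its size depends on an assumed stop rate (power at HR 0.5 falls by 12 points, 47.5% to 35.5%, if 30% stop). Bias is a conditional risk. It needs unequal and prognosis-linked stopping together, and under the assumptions tried it ranges from negligible to an apparent hazard ratio of about 0.7 with a false-positive rate of about 12%. Only secondary endpoints are affected: the primary imaging endpoint at day 21 (± 14 days) does not use this follow-up. The change is worth making because it is cheap, but the main result does not depend on it.

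**What to change.** In 3.4 and 5.7, with the synopsis brought into line, state that for Part B patients who stop the inhibitor without progression, the study continues to abstract three items from the chart: standard-of-care staging results, the start of any new therapy, and vital status. This runs until progression, death or study close and adds no study scans or visits.

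In 7.8.3:

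- Report PFS and 24-week clinical benefit both regardless of discontinuation and on-treatment (stops censored for PFS).
- State in advance which of the two is the main analysis.
- State how patients who stop before week 24 without a response are counted.
- Tabulate stops without progression by imaging group, with reasons, so that a reader can see whether the conditions for bias are present.

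The cost is chart abstraction for a subset of 30 patients: 6 at a 20% stop rate, 9 at 30%. The downside is that the analysis regardless of discontinuation will include some time off drug or on later therapy. Recording new therapy and reporting both versions makes that visible.

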3.5 Study Termination

The principal investigator reserves the right to terminate the study at any time.

Termination of the study will be considered in the event of any safety concerns arising at any time during the performance of the study.

If it becomes necessary to consider termination of the study after dosing has begun, dosing may be suspended pending discussion between the investigators and the DSMC.

4 Investigational Medicinal Product

4.1 Description, Supply and Storage of Investigational Medicinal Product

4.1.1 Hyperpolarized C-13 Pyruvate

¹³C is a stable, non-radioactive isotope of carbon with approximately 1% natural abundance.C-13 pyruvate has exactly the same chemical characteristics as pyruvate. In C-13 pyruvate, either the C-1 or C-2 atom has been replaced by a ¹³C-nucleus, which has a magnetic moment and can be hyperpolarized in the presence of an EPA, i.e., AH111501 sodium salt (a stable trityl radical) by DNP. As C-13 pyruvate has the same chemical characteristics as pyruvate, it is metabolized the same way. However, the fact that it can be hyperpolarized means that MRSI can be used to rapidly detect the hyperpolarized ¹³C-label in C-13 pyruvate and its metabolites, alanine, lactate, bicarbonate, and other metabolites of the TCA cycle such as glutamate.

Formulation

The formulation of IMP in this study will be compounded using 250 mM C-13 pyruvate and up to 3 μ M AH111501 sodium salt. The osmolality of this formulation is ~500 mosmol/kg. After compounding is completed, a sterile fluid path will be pre-filled with the IMP under aseptic conditions. The sterile fluid path itself will be manufactured and cleaned under aseptic conditions in accordance with GMP guidelines (ISO level 7). The pre-filled sterile fluid path and automated hyperpolarizer/quality control instrument (GE SPINLabTM) placed in an adjacent room to the MR suite, will then be used to generate the final hyperpolarized C-13 pyruvate contained within a syringe for rapid injection into the patient (see preparation methods below).

The IMP will be intravenously injected at a rate of 5 ml/second followed by a 20-ml saline flush at 5 ml/second. Prior to dosing, the injection line will be primed with saline solution and some of this will be flushed into the subject ahead of the IMP. In the case of unforeseen events, such as difficulties with the power injector, etc., hand injection will be allowed.

Supply and Packaging

Shipments containing kit supplies for IMP compounding will be provided by the manufacturer and shipped from their clinical supply unit. Site personnel at the clean room will be responsible for receiving kit supplies, compounding the IMP, filling the sterile fluid path using aseptic technique, performing quality control using the GE SPINLabTM instrument, and performing drug accountability. See preparation methods (below) for more information.

Storage

The investigators are responsible for ensuring that deliveries of IMP and other study materials from the manufacturer are correctly received, recorded, handled, and stored safely and properly in accordance with all applicable regulatory guidelines, and used only in accordance with this protocol. The pre-filled sterile fluid paths will be stored at <-20 degrees C, and thawed prior to clinical use.

Preparation Methods

IMP will be compounded under the supervision of a trained pharmacist, using a mixture of ¹³C-pyruvic acid and AH111501 sodium salt. The mixture will be used to pre-fill a sterile fluid path using laser welding technique under aseptic conditions. The pre-filled sterile fluid path will

be stored frozen at <-20 degrees Celsius until the time of clinical use in the Surbeck imaging lab on the Mission Bay campus. At the time of clinical use, the sterile fluid path will be thawed using a warming module housed within the SPINLab™ instrument.

The hyperpolarization process will utilize the automated GE SPINLab™ hyperpolarizer, which is situated in a room adjacent to the MR suite. The mixture of ¹³C-pyruvic acid and AH111501 sodium salt will be hyperpolarized by DNP at low temperature (<1 degree K) using a 5T magnet and zero-helium loss cryogenics system. Following hyperpolarization, the IMP will be dissolved in sterile fluid water, filtered to remove AH111501 to a level below 3 μM, diluted and neutralized with TRIS/EDTA buffered hydroxide solution, all in an automated fashion using the prefabricated sterile fluid path and SPINLab[™] system. An integrated quality control (QC) system will analyze the IMP for pH, temperature, concentration, and polarization level, before it is approved for use by the pharmacist. A sample of IMP will be collected for sterility testing. The final IMP is automatically collected within a syringe. The yield is expected to be ~40 mL of 250 mM ¹³C-pyruvate. Following approval for use from the pharmacist, the syringe containing IMP is delivered to the MRI scanning room and connected to the tubing connected to the infusion pump. The appropriate injection volume is then delivered via the infusion pump to the subject at a rate of 5 ml/second. Note that for different shipments of ¹³C-pyruvate, the concentration may be slightly different than 250 mM. If a slightly different concentration of ¹³C-pyruvate is available. the appropriate injection volume will be different but the amount of ¹³C-pyruvate injected will be unchanged. If this course of action is taken, the updated injection volume will be placed in each patient's chart so that it is clear exactly what concentration and volume the patient received.

The IMP is a colorless to slightly colored, clear liquid.

Warning: Do not use the IMP if any particulates are visible in the solution.

Disposal: Unused substances can be disposed of by flushing down a normal sink using tap water.

Safety Information

Earlier studies of nonhyperpolarized pyruvate outside of the United States were summarized in the background section.

Reported IMP-related AEs in previous studies in humans include:

Cardiovascular: dizziness, catheter site hematoma, heart rate increased, hypertension

Constitutional symptoms: hypoesthesia, unresponsive to stimuli, feeling hot/flushing, fatigue, feeling abnormal

Gastrointestinal: dysgeusia, dry mouth

Genitourinary: micturition urgency

Pain: catheter site pain

Pulmonary: pharyngolaryngeal pain

Neurologic: headache (migraine), parosmia

However, the quality of these prior studies was unclear. The toxicity of the phase I study, which included comprehensive safety monitoring, is summarized in the Background section.

The dosage of IMP that will be used in this study, and the injection rate of 5 ml/second, have been shown to be safe and well tolerated in the phase I study completed at UCSF. Safety monitoring included continuous lead 2 EKG monitoring for 10 minutes after injection, monitoring of vital signs, injection site, EKG, and adverse events, and laboratories for two hours after injection. Patients were also evaluated clinically 24 hours and 7 days after injection. No safety concerns were observed.

4.2 Drug Accountability

The Investigational Pharmacist will manage drug accountability records.

4.3 Drug Ordering

UCSF will obtain supplies for IMP compounding directly from the manufacturer as study supply.

5 Study Procedures and Observations

Schedule of Procedures and Observations

A written, signed, informed consent form (ICF) and a Health Insurance Portability and Accountability Act (HIPAA) authorization must be obtained before any study-specific assessments are initiated. A copy of the signed ICF will be given to the subject and a copy will be filed in the medical record. The original will be kept on file with the study records.

All patients who are consented will be registered in OnCore[®], the UCSF Helen Diller Family Comprehensive Cancer Center Clinical Trial Management System (CTMS). The system is password protected and meets HIPAA requirements.

A list of study subjects will be completed, and will include each subject's study number and initials. The investigator must also maintain a separate log of all the subjects screened for participation in the study but who will not participate, the reasons for their exclusion or non-participation, their initials, and the date on which the subject was excluded.

5.1 Screening Assessments

- The Screening procedures and assessments must be completed within 28 days of baseline MR scan except for staging scans which need to be completed within 12 weeks of baseline MR.
- Physical examination This will include assessment for the presence of abnormalities in general appearance, lungs, cardiovascular system, and abdomen.
- Vital signs including heart rate and blood pressure
- Complete medical history and demographic information
- Baseline conditions assessment
- Concomitant medications
- Disease assessment
- Performance status
- Laboratory procedures
 - Complete blood count (CBC) with differential
 - Blood chemistry assessment including creatinine, AST, ALT, total bilirubin, and lactate dehydrogenase (LDH)
- Electrocardiogram (ECG)
- Staging scans cross-sectional imaging of the abdomen/pelvis (CT or MRI; with IV contrast if medically permissible) (within 3 months of baseline MRscan) (chest imaging is optional)
- **Selection of target lesion:** Study investigators will review the results of standard scans to select the target lesion amenable to metabolic imaging with HP C-13 pyruvate and paired tumor biopsy (review for biopsy in Part B only).

5.2 Metabolic MR Imaging

Pre-Scan Evaluation

Vital signs (systolic and diastolic blood pressure, heart rate) will be monitored at screening and baseline (immediately before the subject is transferred to the MR suite).

Before vital signs are measured, the subject should be resting for at least 5 minutes (if possible). The same position will be used each time vital signs are measured for a given subject and blood pressure will be measured from the arm contra-lateral to the site of IMP administration whenever possible.

Standard MR scanning

Patient is transferred to the MR suite. High spatial resolution MRI to visualize the target lesion using appropriate radiofrequency coil will be performed with axial and coronal T1 and T2 ¹H fast spin echo MRI. Gadolinium contrast will be administered intravenously and contrast-enhanced images will be obtained.

Hyperpolarized C-13 Injection and Dynamic ¹³C MR imaging

Next, hyperpolarized C-13 pyruvate will be injected intravenously at a rate of 5 mL/second followed by a 20 mL saline flush at 5 mL/second.

1-2 minutes post-injection

- Dynamic ¹³C MRI
 - ¹³C 3D MRSI sequence with Multiband spectral-spatial excitation pulse for minimal [1-¹³C]pyruvate saturation and echo-planar spectroscopic imaging (EPSI) readout for accelerated spectral-spatial sampling.
 - $_{\odot}$ The pre-selected target lesion will be imaged on a GE 5T system with parameters typically being T_{E} = 3ms, T_{R} = 125ms, 10 Hz spectral resolution, 581 Hz spectra bandwidth, 8 (PE) x 18 (EPSI) matrix, 5x5 mm resolution, 5mm slice thickness, and 5 s per image. The sequence will be started 5 sec after completing the injection (including catheter flushing) of 250mM HP pyruvate (dose = 0.43 mL/kg, 20 to 45 cc's).
 - A "clamshell" volume ¹³C transmit and/or external RF coils will be used for signal excitation and reception.
 - A second hyperpolarized C-13 injection and dynamic 13-C MRI scan may be performed within 15 to 60 minutes following completion of first scan.. This repeat injection and scan is optional.

Post-injection safety monitoring:

Vital signs (blood pressure and heart rate), adverse event assessment, and injection site monitoring will be performed at 30 minutes post-injection.

Reporting of MR Findings:

The HP C-13 pyruvate/MR scan is considered a research test and as such, will not be used in the clinical management of patients enrolled on the study. A trained radiologist will review all images within 24 hours of scan completion. If there are any unexpected clinically relevant

abnormal findings, these results will be communicated to patient and treating health care provider with 24 hours of completion of MR scan.

